8. STUDY-WIDE RECRUITMENT METHODS*

We will recruit smokers over 48 months. Recruitment will be conducted by both clinic staff and community health workers. We will recruit men and women, and plan for recruiting 15% women. The study will be conducted in the Red River Delta Region, an agriculturally rich and densely populated area in northern Vietnam, with most of the region devoted to the cultivation of rice. In this region, communes in Hung Yen province were selected based on their general representativeness. Hung Yen province has a population of about 1.2 million, organized into 10 districts and 161 communes. All communes in Hung Yen province have adequate electricity. Data from a national survey in 2010 showed that 94% of households in Hung Yen province have a television, and 43% of households have landline phones. Use of text-enabled phones has increased dramatically since 2010. In 2012, a survey found that 84.5% of participants had a mobile phone, and 72.1% of the phones were capable of text messages. Note that although prevalence of text-enabled phones is high, we have budgeted to provide all patients with a phone and cellular service to assure that all eligible smokers can participate.

INVESTIGATOR STUDY PLAN - REQUIRED

Four communes (Xuan Quan, Viet Hung, Tan Viet and Bach Sam) located in four different districts in Hung Yen province will be included based on their general representativeness to the rural northern Vietnamese population, and because we have developed infrastructure to support technology-assisted behavioral interventions through community health centers (CHCs) in these communes. Each of the selected communes satisfy the following criteria: (1) have a community health center with a medical doctor; (2) are not currently participating in other studies for smoking cessation; and (3) have a minimum geographic separation of 12 kilometers (7 miles) from all other study communes to minimize possible contamination.

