Randomization: Participants will be blinded to randomization. All smokers will be told that they will be randomized to one of two different ways to support thinking about quitting smoking. In addition to our primary points of innovation, we will use an innovative mHealth randomization strategy. Allocation of participants to study arms will be based on a permuted block scheme in which treatment assignments are made within blocks so that numbers assigned to each treatment arm are equal after a block has been filled. Blocks of various sizes (2, 4, 6) will be used in random order to facilitate allocation concealment. Similar to our prior technology-based trials, we will embed randomization within the technology. At enrollment, study staff will conduct a baseline survey with participants. At the end of the baseline assessment survey, study staff will enter the participant ID and participant mobile phone number from the survey into our texting system, and the system will look up the next allocation within the table, and adapt based on the allocation assignment. Using this technique, both smokers and the study staff will be blinded to allocation during the initial session. In our prior technology-assisted randomized trials, we have embedded randomization within the technology.

INVESTIGATOR STUDY PLAN - REQUIRED

Baseline data collection (see M2Q2_Baseline_Survey): will include patient demographics, comorbidities, cessation treatment beliefs scale, and self-efficacy. Self-efficacy will be measured with the SEQ-12.^[36] The SEQ-12 is a 12-item questionnaire with 6 questions pertaining to internal stimuli and external stimuli domains each. Two composite scores are computed for each of these domains by adding the individual items. Self-efficacy will be assessed at baseline and follow-up.

Measures through texting: as described above, we will have data collected through texting, including measure of readiness to quit, abstinence assessments, and interest in use of the quitline.

Quitline referral tracking – quitline staff will record details of intake assessment (time on call, readiness to quit, quit date and goal-setting) and fidelity of follow-up call completion. They will also document distribution of NRT lozenge and smoker use of NRT during follow-up.

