13. DATA ANALYSIS AND MANAGEMENT*

Power calculations are based on having complete data on a sample of 600 for the intent-to-treat analysis. Note that for our analysis with missing = smoking, we will use the full sample randomized. As discussed above, all participants randomized to the intervention will receive the motivational messages. However, participants will choose whether or not to use the quitline and NRT.

Our calculations are based on several assumptions. First, in the U.S., rates of cessation without intervention have been documented to be 7-10% per year.^[38] In Vietnam the rate of smoking is high, and the annual rate of cessation is low. To be conservative, we have estimated the control cessation rate to be 10%. Based on our prior trials, we have detected a 9% difference in intervention and control, comparing the motivational messaging system with a robust, website-only control (as we have a simple attention control in this study, the difference may be greater). If we anticipate that 30% of the intervention will engage in quitline counseling and NRT, and that group will have a greater cessation rate (between 20 to 25%), then the overall cessation rate averaged across the intervention group will be greater than 10%. Based on these assumption, we have assessed power for a range of assumptions (with difference in cessation from 7% to 10%). We are powered to detect a 10% difference (alpha at 0.05) with 91% power.

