To preserve the power of randomization, all primary analyses will be on an intent-to-treat basis. However, secondary analyses will explore dose-response effects among those with variable levels of adherence to the intervention. All analyses will be two-sided and alpha error will be set at 0.05. We will begin the statistical analysis by examining univariate statistics (means, medians, standard deviations and 95% confidence intervals) and distributions. We will examine the balance of participant characteristics by study groups and account for any imbalances in our multivariable analysis. As appropriate, group differences will be tested using chi-square tests of independence (categorical variables), Z-test or t-test (continuous variables) or the equivalent non-parametric tests depending on the distribution of the variables. In accordance with best practice, differences in baseline characteristics of the intervention and comparison groups will be established based on standardized differences, rather than on tests of statistical significance.^[39, 40]

Main outcome: six-month point prevalence cessation: The main dependent variable is patient tobacco cessation rate (quit rate). The primary independent variable is assignment to intervention or control group. We have designed a patient-level

INVESTIGATOR STUDY PLAN - REQUIRED

analysis around point prevalence cessation. We will use a two-sided chi-square test for equality of proportions to test whether the quit rates differ between the groups. If we need to adjust for any covariates, we will include them in a multivariable logistic regression model with smoking cessation as the outcome and group status as the main independent variable.

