Dealing with missing outcomes data: We will make every effort to maximize participant retention in the study. For our short-term evaluation, we do not expect high rates of attrition; however, we approximate that there will be about 15-20% attrition based on previous studies. Thus, although we plan to randomize 750, our power calculations for outcomes are based on 600 completing follow-up. We will monitor recruitment and retention, and inflate our sample as needed to achieve the resulting sample of 600 completing 6-months. We will estimate potential bias due to drop-outs in our study and perform a series of sensitivity analyses to understand the extent of this bias. We will assess the extent of missing data by treatment group for each time point. A challenge for all cessation induction trials is missing outcome data.^[43-45] This is especially true in light-touch technology-assisted interventions. Most often, a complete case or missing case (penalized imputation) indicative of smoking analysis has been implemented in logistic regression. However, the reason that we did not use penalized imputation as the primary outcome is that new literature has been published suggesting that penalized imputation (or missing=smoking) is not a conservative approach, and can be biased toward the intervention.^[44] Thus, for studies with missing cessation data greater than 10-20%, experts recommend using selection models to examine the robustness of findings.^[43] We will compare characteristics of patients who remained in the trial and those lost to follow-up. Using a generalized linear model with a logit link to evaluate cessation outcomes and GEE methods to account for clustering within practices, we will

INVESTIGATOR STUDY PLAN - REQUIRED

implement a selection model using inverse probability weighting to determine the potential effect of missing data. First, based on covariates available within the dataset, we will develop a logistic regression model to predict the amount of missing data. Then, we'll calculate the inverse probability of not being missing and weight the main analysis by this probability.^[46]

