In local clinical services in Vietnam, the health system is organized into four levels, namely central, provincial, district hospital, and the lowest level, which includes the CHCs that are responsible for providing primary health care and outpatient services. Patients who smoke are typically treated and managed at the CHC. Based on national benchmarks, a CHC typically has 5 staff members including a medical doctor, an assistant doctor, an OB-GYN nurse, a midwife, and a nurse. Usually, there is one CHC for a commune. As an extended arm of the CHC, community health workers, regulated by the Ministry of Health,^[49] serve as liaisons between the health center and the community. Three quarters of all communes in Hung Yen province meet national benchmarks for CHCs and all have at least one community health care worker.^[50]

Because an established infrastructure of community health workers exists throughout Vietnam and in our proposed study communities, we will build upon this important resource for health education in this population. Previous work by [name] and his team focused on community health worker programs for diabetes in the U.S. revealed several implementation problems including fidelity of intervention delivery and the need for more resources by community health workers.^[51] Similar sentiments were echoed by our formative work in Vietnam.

INVESTIGATOR STUDY PLAN - REQUIRED

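### The weighted missing-data model clusters on practices, of which there are only about four; the usual GEE robust test would then reject about 18–21% of the time at a nominal 5%

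*Combined protocol and SAP*

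**What the plan says.** Under the missing-outcomes heading of section 13, the plan expects substantial dropout: "we approximate that there will be about 15-20% attrition based on previous studies". To examine its effect, it will fit a logit-link model for cessation, use "GEE methods to account for clustering within practices", and "implement a selection model using inverse probability weighting to determine the potential effect of missing data". It does not define practices, say how many there are, or state a working correlation, variance estimator, small-sample correction or reference distribution.

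The number of sites comes from elsewhere. Section 8 names four communes, "located in four different districts in Hung Yen province will be included". Section 22 adds: "Usually, there is one CHC for a commune". Randomisation (section 11) is of individuals: "Allocation of participants to study arms will be based on a permuted block scheme". No stratification by commune is stated. The primary test is an unclustered two-sided chi-square. On error rates, section 13 says "All analyses will be two-sided and alpha error will be set at 0.05".

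**The concern.** The sandwich variance in GEE is estimated from variation between clusters, and its justification needs many of them. With about four, it rests on four terms. It is then too small on average and very unstable from one data set to the next, so some intervals are far too narrow and others too wide.

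The weighted model is the check the plan specifies for dropout of 15–20%. Section 13 itself warns that counting missing participants as smokers can favour the intervention, which gives this check more weight. If its test rejects a true null about one time in five, neither a significant nor a non-significant weighted result says much about whether the finding survives dropout.

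The clustering is also not needed for the treatment comparison. Both arms are present in every commune because individuals are randomised, so commune differences largely cancel from the contrast.

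**Working it through.** **Inputs from the documents.** Four communes (section 8), usually one health centre each (section 22); 750 randomised, 600 completing, 15–20% attrition, two-sided alpha 0.05 (section 13); permuted blocks of 2, 4 and 6 (section 11). For the control rate, section 13 says "we have estimated the control cessation rate to be 10"%.

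**Inputs assumed.** Practices are commune health centres, so K = 4. Commune ICC 0, 0.02 or 0.05 (latent scale). Commune shares equal or 40/30/20/10. One covariate predicts quitting (log OR 0.5) and being observed (log OR 0.4; in an informative-dropout setting, 0.8 in the intervention arm only).

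**1. The plan's own figures.** 600/(1 − 0.20) = 750, as stated. For 10% v 20% with 300 per arm, the continuity-corrected effective size is 300 × (1 − 1/(300 × 0.10))² = 280.3, giving 91.5% power against the stated 91% (93.1% without the correction). The plan gives no operating characteristics for the weighted model.

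**2. Theory with K equal clusters.** The estimate behaves like a mean of K independent cluster contributions. The uncorrected sandwich divides by K where K − 1 is needed, so the test rejects when |t(K−1)| > 1.96 × √((K−1)/K). For K = 4:

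- Uncorrected SE, normal reference: P(|t(3)| > 1.697) = 18.8%.
- Variance × 4/3, normal reference: P(|t(3)| > 1.96) = 14.5%.
- Uncorrected SE, t(3) reference: P(|t(3)| > 3.182 × √(3/4) = 2.756) = 7.0%.
- Variance × 4/3, t(3) reference: 5% by construction.

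The ratio of estimated SE to true SD behaves like √(χ²(3)/4): mean 0.80, 5th percentile √(0.352/4) = 0.30, 95th percentile √(7.815/4) = 1.40.

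**3. Simulation of the weighted model.** 10,000 null trials per setting, independence logit GEE, weights from a logistic model for being observed and treated as known:

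| Method | Type I error |
|---|---|
| GEE, uncorrected SE, normal | 18.3–20.8% |
| GEE, variance × 4/3, normal | 14.1–16.3% |
| GEE, uncorrected SE, t(3) | 6.5–8.1% |
| GEE, variance × 4/3, t(3) | 4.5–5.9% |
| Participant-level robust SE, commune fixed effects | 4.7–5.2% |
| Participant-level robust SE, no commune term | 4.5–5.1% |

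By setting, the first row is 18.3, 18.4 and 19.3% (equal shares; ICC 0, 0.02, 0.05), 20.5 and 20.8% (unequal shares; ICC 0, 0.02) and 19.0% (informative dropout). Monte Carlo SE is about 0.4 points at 19% and 0.2 at 5%. Interval coverage for the first row is 79–82%. The uncorrected SE averages 75–80% of the true SD, with 5th percentile 26–30% and 95th percentile 136–141%, as theory predicts.

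**4. Repeat calculations.** A separately coded simulation gave 17.3–21.0% in ordinary settings and 23.1% with very unequal communes (75/125/225/325, ICC 0.05). Standard GEE software gave 18.6–21.1% across runs, with similar results for independence and exchangeable working correlation.

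**5. Effect on conclusions.** From the same weighted estimate, the usual GEE SE and the participant-level SE disagreed on significance in 15–17% of null trials. In the informative-dropout null setting, the complete-case chi-square was falsely significant in 6.2% of trials. The weighted participant-level model was non-significant in 37% of those; the usual GEE in 21%. Where the chi-square was not significant, GEE was significant in 15% against 1%. These last figures depend on the assumed dropout pattern and are only illustrative.

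**6. If practices meant more units.** The formula in step 2 gives 10.9% for 8 clusters, 7.1% for 20 and 6.0% for 40.

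**The case against.** **One variance option is at fault, not GEE as such.** This is correct. With weights scaled to mean 1, GEE's model-based SE rejected in 4.0–4.7% of null trials. But it has no general guarantee under weighting and depends on how the weights enter. With unscaled weights averaging 1/0.8 = 1.25, the expected rate is P(|Z| > 1.96/√1.25 = 1.753) = 8.0%, and weighted runs in standard software gave 7.4–8.2%. The plan names no option, and the choice moves the rejection rate from about 5% to about 20% on the same data. That is a reason to specify it.

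**Four is inferred.** This is also correct. Section 22 describes the health system generally, and section 11 samples adults from commune lists and recruits through community health workers as well as clinics, so a participant need not belong to any practice. Still, the documents describe no other unit that fits, and an undefined clustering unit itself needs correcting.

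**The text can be read another way.** The same paragraph ends by saying that the main analysis will be weighted, and the main analysis is not clustered. That reading is close to the fix below, but it conflicts with the explicit GEE clause.

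**It is only a sensitivity analysis, and robustness can be judged by comparing estimates.** Both are true and limit the severity. The plan does not say that robustness will be judged on significance alone. But an interval that covers about 80% also misleads a reader who looks only at estimates and their precision.

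**Conclusion.** The concern holds. If practices are the commune health centres and the usual uncorrected robust test is used, a nominal 5% test of the weighted model rejects about 18–21% of the time. The figure is about 18–19% even at ICC 0 with equal communes, so it does not rest on an assumed ICC; unequal communes make it somewhat worse. It does rest on the reading of practices and on a variance choice that the plan neither names nor rules out. The damage is confined to the standard error, interval and p-value of the missing-data sensitivity analysis. The plan should be changed on this point, but it does not threaten the primary result.

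**What to change.** In the missing-outcomes paragraph of section 13, replace the GEE-by-practice clause with wording such as: *the weighted analysis will be a logistic model for cessation with treatment group and commune (four levels, fixed) as terms, inverse-probability weights, and robust standard errors at participant level.* This also settles the conflict with the sentence about weighting the main analysis. Leave the primary chi-square test as it is.

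**Cost.** One sentence and no new data, since residence in a selected commune is an eligibility criterion. The commune term uses three degrees of freedom and makes the odds ratio conditional on commune, so slightly less comparable with the unadjusted primary result: mean log OR 0.823 against 0.815 at 10% v 20%, ICC 0.02. Omitting the term, or reporting a standardised risk difference, avoids this. State that the term is dropped if a commune has no observed quitters, since its coefficient then cannot be estimated.

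**If GEE by commune is kept.** Define practices, and pre-specify a small-sample-corrected variance with a t(3) reference. Correcting the variance alone is not enough (14.1–16.3%). The price is intervals about 1.4 times as wide. A true 10% v 20% difference is then significant in 63% of trials against 94% for the participant-level model, and 10% v 17% in 41% against 72%.

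### The only robustness method specified for missing cessation outcomes is a missing-at-random analysis, so it cannot show how sensitive the result is to dropout that depends on smoking and differs by arm

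*Combined protocol and SAP*

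**What the plan says.** The relevant text is the paragraph on missing outcomes in Section 13. It expects attrition of about 15-20%. It declines to make missing = smoking the primary approach, because that rule may not be conservative and may favour the intervention. It then says that, when more than 10-20% of cessation data are missing, "experts recommend using selection models to examine the robustness of findings".

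The method that follows is to "implement a selection model using inverse probability weighting to determine the potential effect of missing data". Its first step is that, "based on covariates available within the dataset, we will develop a logistic regression model to predict the amount of missing data". Its second is to weight the main analysis by the inverse of the estimated probability of being observed.

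Three other statements matter:

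- The opening of Section 13 keeps a missing = smoking analysis on everyone randomised.
- The missing-outcomes paragraph promises several sensitivity analyses, an account of missingness by treatment group, and a comparison of completers with dropouts. Apart from the weighting, it does not say what the sensitivity analyses are.
- Section 11 says that text messages will collect readiness to quit and abstinence during the trial. They are not named as covariates for the weights.

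**The concern.** The plan doubts missing = smoking because of what it assumes about the smoking status of people who are not seen, and because the error may favour one arm. The method put forward to test robustness does not vary that assumption. It has no term for the unobserved outcome and no sensitivity parameter. It takes missing participants to have the quit rate of observed participants with the same covariates.

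If smokers are more likely to disappear, and more so in one arm, the weighted and unweighted results can agree closely while both are biased. A reader could take that agreement as reassurance on a question the method does not address. With up to a fifth of outcomes missing, this can decide whether a modest effect is believed.

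**Working it through.** **Inputs from the plan.** Sample size: "although we plan to randomize 750, our power calculations for outcomes are based on 600 completing follow-up". Allocation is equal, since "numbers assigned to each treatment arm are equal after a block has been filled". That gives 375 randomised and 300 observed per arm, with missing fraction m = 0.20. At 15% attrition, 375 × 0.85 is about 319 observed per arm. The control quit rate is 10%, and Section 13 considers differences of 7 to 10 points, so the intervention rate is 17% to 20%. Tests are two-sided at 0.05.

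**Assumed input.** Let r be the odds of smoking in missing participants divided by the odds in observed participants, set separately by arm. The documents give no value for r.

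**The plan's own figures.** For 10% vs 20% with 300 per arm, the continuity-corrected normal approximation gives 91.5% power, against the stated 91%; without the correction it is 93.1%. Also, 600 / 0.80 = 750. The inputs are therefore read as the plan intends.

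**What the weighting does.** Weights of 1 / P(observed given covariates) give missing participants the quit rate of observed participants with the same covariates, so r = 1 within covariate strata by construction. A check used 375 per arm, 20% missing per arm, and one observed covariate with an assumed odds ratio of 2 on both quitting and response.

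| Scenario | True difference | Complete case | Weighted |
|---|---|---|---|
| Dropout depends on covariate only | 10.0 | 10.2 | 10.0 |
| No effect; intervention-arm smokers have 3 times the odds of dropout | 0 | +1.35 | +1.34 |
| No effect; 5 times the odds | 0 | +1.70 | +1.69 |

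In 4,000 simulated trials of the last row, the nominal 5% test rejected in 10.2% (complete case) and 10.3% (weighted). Missing = smoking gives an expected +1.36 points in that row, so it does not recover the null either. The weighting does its job when data are missing at random and follows the complete-case bias when they are not.

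**Size of the shift.** Full-sample rate = (1 − m)p + mq, where q = o / (1 + o) and o = [p / (1 − p)] / r.

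Observed 20% vs 10%, m = 0.20:

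- r = 5, intervention only: o = 0.25 / 5 = 0.05, q = 0.0476; 0.16 + 0.2 × 0.0476 = 16.95%. Difference 6.95 points.
- All missing intervention participants smoke: 16% vs 10%. Difference 6.0 points.
- r = 5, control only: o = 0.1111 / 5 = 0.0222, q = 0.0217; 0.08 + 0.0043 = 8.43%. Difference 11.57 points.

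A pooled two-proportion test gives p = 0.005 for the first and 0.015 for the second with 375 per arm, or 0.013 and 0.029 with 300. Both stay significant.

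Observed 17% vs 10%, the lower end of the plan's range:

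- As observed, 300 per arm: SE = √(0.135 × 0.865 × 2/300) = 0.0279; z = 2.51; p = 0.012.
- All missing smoke in both arms, 375 per arm: 13.6% vs 8.0%; SE = √(0.108 × 0.892 × 2/375) = 0.0227; z = 2.47; p = 0.013.
- All missing smoke in the intervention arm, control dropout random: 13.6% vs 10%; SE = √(0.118 × 0.882 × 2/375) = 0.0236; z = 1.53; p about 0.13.
- With control dropout random, r = 2 in the intervention arm gives 15.5% (p = 0.025) and r = 5 gives 14.4% (p = 0.066). Significance is lost at r of about 3.5.

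The tests on 375 per arm treat filled-in outcomes as if observed, so these p-values are somewhat too small.

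**False-positive rate.** Fix the true rate at 10% in both arms and let control dropout be random. Solve (1 − m)p + mq = 0.10 for the observed intervention rate p, then find how often it differs significantly from 10%.

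| Attrition | r | Observed intervention rate | Rejection |
|---|---|---|---|
| 15% | 5 | 11.3% | 8.4% |
| 15% | 10 | 11.5% | 9.6% |
| 20% | 2 | 11.0% | 7.0% |
| 20% | 5 | 11.8% | 11.2% |
| 20% | 10 | 12.2% | 13.4% |

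**The case against.** The best defence is that weighting is not the only analysis. Missing = smoking is declined only as the primary approach and kept as a secondary one, and it does depend on the outcome. More sensitivity analyses are promised, and missingness will be described by arm. A reader might infer that robustness would be declared on the weighting alone; the plan does not say so. What remains is that missing = smoking is a single setting applied equally to both arms, which the plan itself suspects of bias, and that no named analysis varies the assumption by arm.

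A reader might also infer that a better method would detect outcome-dependent dropout. None can do so from the observed data. A pattern-mixture analysis shows only how far the conclusion depends on what is assumed.

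The purpose of the check is partly inferred. The plan does not name outcome-dependent dropout, and weighting can loosely be placed among selection models. The label is therefore secondary; the substance is the absent outcome term.

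Nor is it right that weighting cannot move the result. If text-message abstinence replies were used as covariates, part of the bias could be removed. The plan neither commits to this nor rules it out, and participants who stop replying may lack those data.

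Finally, the plan's 10-point scenario survives the cases above, and the larger error rates need strong dropout effects in one arm only. Both points stand and limit the severity.

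**Conclusion.** The concern holds in a limited form. The one robustness method that is spelled out assumes missing at random, and nothing specified shows sensitivity to smoking-related dropout that differs by arm. This does not invalidate the primary test, and an effect near 10 points would probably withstand such dropout. An effect near 7 points might not: under the most adverse intervention-arm assumption, p moves from 0.012 to about 0.13, while missing = smoking in both arms leaves it at 0.013. The false-positive rate could reach about 8-10% at 15% attrition and 11-13% at 20%, for r of 5 to 10 in the intervention arm only. Bias in the other direction is equally possible if control-arm smokers are the ones lost. All of these sizes depend on assumed values of r.

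One open point could make this matter more. Section 11 provides no carbon monoxide test for telephone interviews, and the plan does not say how unverified reports of abstinence are classified. If they count as missing while telephone reports of smoking count as known, missingness depends directly on the reported outcome.

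**What to change.** In Section 13:

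- Call the inverse probability weighting the missing-at-random sensitivity analysis, and list its covariates, saying whether text-message abstinence and readiness replies are included.
- Keep missing = smoking as one scenario among several.
- Prespecify a pattern-mixture analysis that varies the odds ratio of smoking in missing versus observed participants separately by arm, for example 1, 2, 5 and all smoking. Report the estimate and confidence interval for each combination, and the tipping point at which the arm difference loses significance.
- State how telephone respondents who report abstinence are classified.

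The cost is SAP wording and a short extra analysis on data already being collected. The downside is small: a positive result may be shown to be less robust than it looks.
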